#### **9.4.4. Relationship to Investigational Product**

The relationship of an AE to the study drug should be determined by the Investigator according to the following definitions:

**NOT RELATED:** Evidence exists that the AE has an etiology other than the study drug and/or the temporal relationship of the AE/SAE to the investigational product administration makes the relationship unlikely. If an SAE is not considered to be related to study drug, then an alternative explanation should be provided.

**RELATED:** A temporal relationship exists between the event onset and the administration of the study drug and makes a causal relationship possible or probable. It cannot be readily explained by the participant’s clinical state or concomitant therapies and may appear, with some degree of certainty, to be related based on the known therapeutic and pharmacologic actions of the drug. Good clinical judgment should be used for determining causal assessment.

#### **9.4.5. Unexpected Adverse Reactions**

An adverse reaction is “unexpected” if its nature and severity are not consistent with the information about the study drug provided in the PF-07940367 IB (Pfizer, 2023).

#### **9.4.6. Adverse Event Reporting**

##### **9.4.6.1. General AE Reporting**

All AEs/SAEs will be recorded from the time the study participant/parent/legal guardian/legally authorized representative signs the ICF/assent form until the EOS Visit or ET Visit, whichever comes first. The AE or SAE must be recorded on the CRF and the SAE reported using PSSA. The Investigator is responsible for evaluating all AEs/SAEs, obtaining supporting documents, and ensuring that documentation of the event is complete. Details of each reported AE/SAE must include at a minimum severity, relationship to study treatment, duration, and outcome.

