Participants will be followed for approximately 12 weeks after completing dosing to further assess safety. Participants should return to the study site for an EOS visit approximately 12 weeks after the last dose of study drug.

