#### 8.2.2. Discontinuation due to Adverse Events

In addition to the dose modification and study stopping rules previously outlined in Section 7.5 and Section 8.1, respectively, any participant who experiences an AE may be withdrawn at any time from the study at the discretion of the Investigator. Participants withdrawn from the study due to an AE, whether serious or nonserious, should be followed by the Investigator until the clinical outcome of the AE is determined (ie, the event has

resolved or has stabilized). The AE(s) should be noted on the appropriate eCRFs. The Sponsor and/or contract research organization (CRO) Medical Monitor must be notified of the study participant discontinuation. If the AE relates to overdose of study treatment, see Section 7.6 for details of specific actions to be taken.

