### 8.3. Discontinuation/Withdrawal from the Study

- A participant may withdraw from the study at any time at their own request or may be withdrawn at any time at the discretion of the Investigator for safety, behavioral, or compliance reasons.
- At the time of discontinuing from the study, if possible, an early discontinuation visit should be conducted, as shown in the Schedule of Assessments (SoA) Section 2.1. The SoA details the data to be collected at the time of study discontinuation and follow-up and for any further evaluations that need to be completed.
- The participant will be permanently discontinued from the study treatment and the study at that time.
- If the participant/parent/legal guardian/legally authorized representative withdraws consent for disclosure of future information, the Sponsor may retain and continue to use any data collected before such a withdrawal of consent.
- If a participant withdraws from the study, they may request destruction of any samples taken and not tested, and the Investigator must document this in the site study records.

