##### **9.4.7. Time Period and Frequency for Collecting AE and SAE Information**

The time period for actively eliciting and collecting AEs and SAEs ("active collection period") for each participant begins from the time the participant/parent/legal guardian/legally authorized representative provides informed consent, which is obtained before undergoing any study related procedure and/or receiving study intervention, through and including a minimum of 63 calendar days after the last administration of the study intervention. Follow-up by the investigator continues throughout the active collection period and until the AE or SAE or its sequelae resolve or stabilize at a level acceptable to the investigator.

When a clinically important AE remains ongoing at the end of the active collection period, follow-up by the investigator continues until the AE or SAE or its sequelae resolve or stabilize at a level acceptable to the investigator and Pfizer concurs with that assessment.

For participants who are screen failures, the active collection period ends when screen failure status is determined.

If the participant withdraws from the study and also withdraws consent for the collection of future information, the active collection period ends when consent is withdrawn.

If a participant permanently discontinues or temporarily discontinues study intervention because of an AE or SAE, the AE or SAE must be recorded on the CRF and the SAE reported using PSSA Pfizer's Serious Adverse Event Submission Assistant. The Sponsor/Medical Monitor(s) must be notified of the study participant discontinuation.

Investigators are not obligated to actively seek information on AEs or SAEs after the participant has concluded study participation. However, if the investigator learns of any SAE, including a death, at any time after a participant has concluded study participation, and they consider the event to be reasonably related to the study intervention, the investigator must promptly report the SAE to Pfizer using PSSA.

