**2.2.3. Study Design**

C5351005 (OLE) is designed as a multicenter, global, open-label extension study. The primary objective is to assess the long-term safety of osivelotor in participants with SCD. This study is available to eligible participants who have previously enrolled in a Pfizer-sponsored osivelotor clinical study and meet the entry criteria for this study.

Eligible participants will receive open-label osivelotor at Baseline (Day 1). It is intended that Day 1 coincides with the final visit from the originating osivelotor study. End of Treatment (EOT) assessments from the originating study will serve as Baseline assessments for this study. If Day 1 for this study is greater than 7 days from the completion of the originating study, new baseline assessments will be obtained. If during the period between Day 1 of this study and completion of the originating study no dose is received for greater than 3 consecutive days, an appropriate loading dose will be administered prior to continued maintenance dosing.

Only participants from C5351004 Part A (also referred to as the “parent study”) were enrolled into the OLE. C5351004 Part A is a study which enrolled only adult participants. There are two sets of participants rolling over from C5351004 Part A to the OLE study – (i) participants without a delayed start (Date of first dose in C5351005 – EOT date from C5351004 + 1 ≤ 42 days) and (ii) participants with a delayed start of OLE (Date of first dose in C5351005 – EOT date from C5351004 + 1 > 42 days). Each set follows a distinct schedule of assessments as outlined in the C5351005 protocol.

**3. ENDPOINTS AND BASELINE VARIABLES: DEFINITIONS AND CONVENTIONS****3.1. Primary Endpoint(s)****3.1.1. Incidence of TEAEs**

A treatment-emergent adverse event (TEAE) is defined as an AE that occurs during the effective duration of treatment defined as the time from the first dose of study drug through last dose of study drug + 56 days.

TEAEs that occur in the parent study are not counted as TEAEs in this study. In case, the start date of AE is the same date as the treatment start date and the question in the AE CRF page “Is this AE continuing from the parent study?” = “Yes”, then the event is not a TEAE,

as long as it can be confirmed that the AE in question had a start date in the parent study and no end date in the parent study.

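### Protocol 9.4.6.1 ends AE recording at the ET visit, contradicting the 63-day post-dose minimum in 9.4.7; where a site applies 9.4.6.1, the TEAE window is cut short for participants who leave the study early

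*Protocol*

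**What the plan says.** Two sections of the protocol's current text say when AE collection ends.

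- Protocol 9.4.6.1 records all AEs and SAEs from consent "until the EOS Visit or ET Visit, whichever comes first". It sets no minimum time after the last dose.
- Protocol 9.4.7 defines an active collection period for each participant, running "through and including a minimum of 63 calendar days after the last administration of the study intervention". It names two early stops. One is screen failure. The other is a participant who leaves the study and also withdraws consent for future information, in which case "the active collection period ends when consent is withdrawn".

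The timing of the visits comes from elsewhere. Protocol 8.3 places the early discontinuation visit at the time of leaving the study, and adds: "The participant will be permanently discontinued from the study treatment and the study at that time". For participants who only stop drug, Protocol 5.1 states: "Participants will be followed for approximately 12 weeks after completing dosing to further assess safety". Protocol 8.2 likewise asks for an EOS visit about 12 weeks after the last dose.

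On the analysis side, SAP 3.1.1 counts an AE as treatment-emergent if it occurs in "the time from the first dose of study drug through last dose of study drug + 56 days". SAP 5.3.1 computes percentages on the number of participants in each dose arm unless otherwise specified.

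**The concern.** Incidence of TEAEs is a primary endpoint. The SAP window assumes that AEs are recorded for 56 days after the last dose, and the 63-day minimum in 9.4.7 would secure that. The stopping rule in 9.4.6.1 would not, because for a participant who leaves the study the ET visit comes first.

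Two consequences follow. Sites reading different sections would collect AEs over different periods for the same kind of participant. Where 9.4.6.1 is applied, the unrecorded part of the window is treated as event-free, because the participant stays in the denominator with no allowance for shorter follow-up.

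**Working it through.** The study tests no hypothesis and its sample size is a rollover count, so there is no power or event figure to reproduce. The check is day arithmetic.

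**Inputs**

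- Minimum active collection: 63 days after the last dose (Protocol 9.4.7).
- TEAE window: 56 days after the last dose (SAP 3.1.1), with the EOT date serving as the last-dose date (SAP 5.1).
- EOS visit: about 12 weeks after the last dose (Protocol 5.1 and 8.2).
- ET visit: at study discontinuation, with no set interval from the last dose (Protocol 8.3).

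**Participants who stop drug but stay in the study.** EOS falls at 12 × 7 = 84 days. This exceeds both 63 and 56, so nothing is lost under either section.

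**Participants who leave the study with an ET visit, under 9.4.6.1.** Let *d* be the days from last dose to ET.

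- Shortfall against 9.4.7 = max(0, 63 − *d*)
- TEAE-window days lost = max(0, 56 − *d*)

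| *d* | Shortfall against 63 days | TEAE-window days lost | Share of the 56 days |
|---|---|---|---|
| 0 | 63 | 56 | 100% |
| 14 | 49 | 42 | 75% |
| 28 | 35 | 28 | 50% |
| 42 | 21 | 14 | 25% |
| 56 | 7 | 0 | 0% |
| 63 | 0 | 0 | 0% |

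The sections therefore conflict when ET is less than 63 days after the last dose, and the TEAE window is cut when it is less than 56 days.

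**Direction of the effect.** The denominator is fixed, so a missing event can only lower a TEAE percentage. It lowers the any-TEAE figure only for a participant with no earlier TEAE. It lowers an SOC or PT row only for a participant with no earlier event in that row.

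**Possible size, on assumed inputs.** The documents give neither a TEAE rate nor the number of early terminations. Suppose ET is on the last-dose day, the participant has had no earlier event in the row, and the event rate *r* is constant. The chance that a first event falls in the unrecorded time is 1 − exp(−*r* × 56/365.25).

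| Assumed *r* per person-year | Chance of a missed first event |
|---|---|
| 0.1 | 1.5% |
| 0.5 | 7.4% |
| 1.0 | 14.2% |
| 2.0 | 26.4% |

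If 10% of participants ended this way, about 0.2 to 2.6 participants per 100 enrolled would have a missed first event (0.10 × 1.5% to 0.10 × 26.4%). If 30% did, the range is about 0.5 to 7.9 per 100. These are illustrations, and they run high for the any-TEAE row because many participants will already have had a TEAE.

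**After the fix.** With at least 63 days recorded for everyone who has not withdrawn consent for future information, the 56-day window is covered with 63 − 56 = 7 days to spare.

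**The case against.** The strongest reply is that 9.4.7 is the section dedicated to the collection period, applies to each participant, and already gives the longer rule. The amendment summary lists it as new in Amendment 4, so 9.4.6.1 may simply be wording that was not updated. A site following 9.4.7 loses nothing. This stands in part: the loss is conditional on which section a site applies. It does not remove the contradiction, because nothing in the protocol says which section prevails.

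A second reply is that 9.4.7 itself supports stopping at ET, since "Investigators are not obligated to actively seek information on AEs or SAEs after the participant has concluded study participation". Read as ending collection at every ET visit, that sentence would leave the separate condition on withdrawn consent with no purpose. It is better read as applying after the active period, but the text does not say so. Nor does a later EOS visit rescue 9.4.6.1, because its rule takes whichever visit is first.

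Several stronger readings are tempting, and the documents do not support them.

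- *Everyone who stops drug early loses follow-up.* Only those who leave the study with a prompt ET visit are exposed.
- *The loss falls mainly on participants who leave because of AEs.* Protocol 8.2.2 says "any participant who experiences an AE may be withdrawn at any time from the study at the discretion of the Investigator", so the route exists, but no document says how often it is used. That section also follows the AE behind the withdrawal to its outcome, so only new AEs are at issue.
- *The lost days measure the bias.* TEAE incidence is a simple proportion of participants, not a rate per person-time, so a share of days lost does not translate directly into a share of events lost.
- *The half-life of about 10 days in SCD sizes the problem.* It describes remaining drug, not missed events.
- *The VOC rate is affected too.* SAP 6.2.1 analyses on-treatment VOCs, with participant-years ending at the EOT date.

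**Conclusion.** The contradiction is real and sits in current text on the collection period for a primary safety endpoint. For a participant who leaves the study with an ET visit less than 63 days after the last dose, 9.4.6.1 and 9.4.7 cannot both be followed. If the site applies 9.4.6.1 and ET is less than 56 days after the last dose, up to all 56 post-dose window days go unrecorded for new AEs. Reported TEAE incidence can then only be too low.

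The number of participants affected is unknown. It depends on how many leave the study, how soon after the last dose their ET visit falls, and which section the site follows. The planned enrolment of about 500 should not be used to scale the loss, because SAP 2.2.3 states that only participants from Part A of C5351004 were enrolled.

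**What to change.** In Protocol 9.4.6.1, replace the EOS-or-ET stopping rule with a reference to the active collection period in 9.4.7: at least 63 days after the last dose, including after an ET visit, unless consent for future information is withdrawn. In 9.4.7, state that the sentence on concluded participation applies only once that period has ended.

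No change to the discontinuation rules in 8.2.2 or 8.3 is needed, and none to VOC collection.

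The cost is protocol wording plus, at most, a remote contact after an ET visit, which 9.4.7 already implies. Reported TEAE incidence may rise slightly. New wording cannot recover events from participants who have already left. For them, a listing in the study report of days from last dose to the end of AE recording would show how much of the window was observed.

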##### **9.4.7. Time Period and Frequency for Collecting AE and SAE Information**

The time period for actively eliciting and collecting AEs and SAEs ("active collection period") for each participant begins from the time the participant/parent/legal guardian/legally authorized representative provides informed consent, which is obtained before undergoing any study related procedure and/or receiving study intervention, through and including a minimum of 63 calendar days after the last administration of the study intervention. Follow-up by the investigator continues throughout the active collection period and until the AE or SAE or its sequelae resolve or stabilize at a level acceptable to the investigator.

When a clinically important AE remains ongoing at the end of the active collection period, follow-up by the investigator continues until the AE or SAE or its sequelae resolve or stabilize at a level acceptable to the investigator and Pfizer concurs with that assessment.

For participants who are screen failures, the active collection period ends when screen failure status is determined.

If the participant withdraws from the study and also withdraws consent for the collection of future information, the active collection period ends when consent is withdrawn.

If a participant permanently discontinues or temporarily discontinues study intervention because of an AE or SAE, the AE or SAE must be recorded on the CRF and the SAE reported using PSSA Pfizer's Serious Adverse Event Submission Assistant. The Sponsor/Medical Monitor(s) must be notified of the study participant discontinuation.

Investigators are not obligated to actively seek information on AEs or SAEs after the participant has concluded study participation. However, if the investigator learns of any SAE, including a death, at any time after a participant has concluded study participation, and they consider the event to be reasonably related to the study intervention, the investigator must promptly report the SAE to Pfizer using PSSA.

##### **9.4.7.1. Diagnosis Versus Signs and Symptoms**

If known, a diagnosis should be recorded on the eCRF rather than individual signs and symptoms (eg, record only liver failure or hepatitis rather than jaundice, asterixis, and elevated transaminases). However, if a constellation of signs and/or symptoms cannot be

medically characterized as a single diagnosis or syndrome at the time of reporting, each individual event should be recorded separately on the eCRF. If a diagnosis is subsequently established, it should be reported as follow-up information.

#### **9.4.7.2. Abnormal Laboratory Values**

Clinically significant laboratory test results will be recorded on the AE eCRF (eg, abnormalities that have clinical sequelae, more frequent follow-up assessments, or further diagnostic investigation). If the clinically significant laboratory abnormality is a sign of a disease or syndrome (eg, alkaline phosphatase and bilirubin  $5 \times$  the upper limit of normal associated with cholecystitis), only the diagnosis (eg, cholecystitis) should be recorded on the eCRF.

If the clinically significant laboratory abnormality is not a sign of a disease or syndrome, the abnormality itself should be recorded on the eCRF. If the laboratory abnormality can be characterized by a precise clinical term, the clinical term should be recorded. For example, an elevated serum potassium level of 7.0 mEq/L should be recorded as "hyperkalemia".

Observations of the same clinically significant laboratory abnormality from visit to visit should not be repeatedly recorded on the AE eCRF, unless their severity, seriousness, or etiology changes.

#### **9.4.8. Serious Adverse Events, Serious Adverse Drug Reactions, and Requirements for Immediate Reporting**

All SAEs, regardless of causal attribution, must be reported by the Investigator/designee or site personnel within 24 hours of SAE awareness on the AE eCRF and reported to Pfizer Safety via PSSA. In the event that PSSA is not available, paper SAE report forms will be used to report the SAE and faxed or emailed to the Sponsor or CRO designee. The information reported on paper SAE report form should be entered into the EDC once available.

The Sponsor or designee may request additional source documentation pertaining to the SAE from the investigational site. Follow-up reports must be submitted within 24 hours of awareness and participant identifier information (eg, name, medical record number) must be redacted in the hospital discharge summaries, autopsy reports, and/or death certificates.

Follow-up SAE information must be submitted within 24 hours of awareness as additional information becomes available. All SAEs regardless of causal attribution must be followed to resolution or stabilization, or until reasonable attempts to determine resolution of the SAE are performed.

##### **9.4.8.1. Reporting Suspected Unexpected Serious Adverse Reactions and Urgent Safety Issues**

The Sponsor is responsible for reporting suspected unexpected serious adverse reactions (SUSARs) to regulatory agencies, competent authorities, IRBs/ECs, and Investigators as per local laws and regulations. Fatal and life-threatening SUSARs will be submitted no later than 7 calendar days of the Sponsor's first knowledge of the event and follow-up information submitted within an additional 8 calendar days, or as otherwise required per local laws and

regulations. All other SUSARs will be submitted within 15 calendar days of the Sponsor's first knowledge of the event. The Investigator is responsible for notifying the local IRBs or ECs of all SAEs that occur at his or her site as required by local regulations or IRB/EC policies, if this responsibility resides with the site.

Investigators are required to report any urgent safety matters to the Sponsor within 24 hours of awareness. The Sponsor will inform regulatory authorities, IRBs/ECs, and Investigators, as applicable, of any events (eg, change to the safety profile of osivelotor, major safety findings that may place study participants at risk) that may occur during the clinical trial that do not fall within the definition of a SUSAR but may adversely affect the safety of study participants.

#### **9.4.9. Drug-induced Liver Injury**

Participants will be monitored for signs of drug-induced liver injury (DILI).

Potential events of DILI will be defined as meeting all the following criteria (as specified in the FDA Guidance for *Drug-Induced Liver Injury: Premarketing Clinical Evaluation 2009* [FDA, 2009]).

Potential events of DILI will be reported as SAEs (Section 9.4.8). All participants with potential DILI will be closely followed until abnormalities return to normal or baseline or until all attempts to determine resolution of the event are exhausted.

See [Appendix 2: Liver Safety: Suggested Actions and Follow-Up Assessments](#) in the event of potential DILI.

#### **9.4.10. Method of Detecting AEs and SAEs**

Care will be taken not to introduce bias when detecting AEs and/or SAEs. Open-ended and nonleading verbal questioning of the participant/parent/legal guardian/legally authorized representative is the preferred method to inquire about AE occurrences.

